5.2.10.1.5 Intensity (severity) of AEs

The intensity (severity) of the AE should be judged based on the following:

- Mild: Awareness of sign(s) or symptom(s) that is/are easily tolerated.
Moderate: Sufficient discomfort to cause interference with usual activity.
Severe: Incapacitating or causing inability to work or to perform usual activities.

In addition the intensity of diarrhoea adverse events should be classified and recorded in the eCRF according to the Common Terminology Criteria for Adverse Events (CTCAE) version 4 ([R10-4848](#), Table 5.2.10.1.5: 1).

Table 5.2.10.1.5: 1 CTCAE Categorisation for diarrhoea

CTCAE Grade	Diarrhoea
1	Increase of <4 stools per day over baseline
2	Increase of 4 to 6 stools per day over baseline
3	Increase of ≥ 7 stools per day over baseline; incontinence
4	Life threatening consequences
5	Death

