7.3.4 Safety analyses

Adverse events will be coded using the Medical Dictionary for Drug Regulatory Activities (MedDRA). Standard BI summary tables and listings will be produced.

The safety analysis will be based on the TS. In general, safety analyses will be descriptive in nature and will be based on BI standards. No hypothesis testing is planned.

The analyses will be done by ‘treatment at onset’.

Statistical analysis and reporting of adverse events will concentrate on treatment-emergent adverse events. To this end, all adverse events occurring between start of treatment and end of the REP (see Section [1.2](#) and Section [5.2.10.2.1](#)) will be considered ‘treatment-emergent’. Therefore, AEs recorded prior to first intake of trial medication will be assigned to ‘screening’, those between first Microgynon[®] intake until end of the REP of Microgynon[®] in Period 1 will be assigned to the Microgynon[®] treatment period. AEs from intake of Microgynon[®] until the end of REP of Microgynon[®] during Period 2 will be considered as on-treatment for Microgynon[®] plus nintedanib. All other AEs during nintedanib treatment up to the end of the trial will be assigned to on-treatment on nintedanib. Events after the end of the REP of Microgynon[®] during Period 1 but prior to the start of nintedanib treatment in Period 2 will be considered as ‘post-treatment’ for Microgynon[®]. AEs after the End of Study (EOS) examination will be assigned to ‘post-study’ unless they are within 7 days after last nintedanib intake. In this event they would be counted as on-treatment for nintedanib. Adverse events that start before first drug intake and deteriorate under treatment will also be

considered as ‘treatment-emergent’. These assignments including the corresponding time intervals will be defined in detail in the TSAP.

Frequency, severity, and causal relationship of adverse events will be tabulated by system organ class and preferred term after coding according to the current version of the Medical Dictionary for Drug Regulatory Activities (MedDRA) at database lock.

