4. CHANGES IN THE PLANNED ANALYSIS OF THE STUDY

As compared to the CTP, the following changed in the planned analysis of this study:

For the display of adverse event data, the time intervals after residual effect periods of treatments have been renamed from 'post-treatment' to 'follow-up' (in contrast to Section 7.3.4 of the CTP).

CTP states in Section 7.3.4: *Treatment groups will be compared descriptively with regard to distribution parameters [of laboratory data] as well as with regard to frequency and percentage of patients with abnormal values or clinically relevant abnormal values.*

This analysis was not adopted by the initial TSAP. Considering the rather sparse time points of safety laboratory sampling, and the absence of samples within the residual effect period of Microgynon® in both treatment periods (as per CTP), the value of a descriptive analysis was considered to be questionable.

CTP states in Section 2.2.1: *Pre-dose (trough) plasma concentration monitoring of steady-state nintedanib will be performed in order to assess whether ethinylestradiol and/or levonorgestrel have an influence on the exposure of nintedanib.* CTP Section 2.2.2 clarifies: *Pre-dose (trough) plasma levels concentration ($C_{pre,ss}$) of nintedanib at steady state will be assessed to prove [nintedanib] exposure.* This TSAP adopts the statement from Section 2.2.2.

As compared to the initial TSAP of this trial, the following changed in the planned analysis of this study:

As specified in CTP Section 5.2.10.2.1, AEs that started after the individual patient's End of Study will not be reported in the eCRF. (For an individual patient who completes the study and will participate in the roll-on Trial 1199-0225, any ongoing AE or new AE that occurs after End of Study must be reported in the roll-on trial 1199-0225.) Therefore, assignment of AEs after the End of Study examination to the "post-study" phase is not applicable. There will be no such AEs in the database and no "post-study" phase in AE analyses. The "post-study" phase defined in Table 6.1: 1 of the initial TSAP was not adopted by this final TSAP.

As specified in CTP Section 7.3.4: *All other AEs [except for AEs from intake of Microgynon® until the end of REP of Microgynon® during Period 2] during nintedanib treatment up to the end of the trial will be assigned to on-treatment on nintedanib.*

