In Table 6.1: 1 of the initial TSAP, a nintedanib follow-up phase was defined, which is not in accordance with the definition quoted above. Therefore, the nintedanib follow-up phase was not adopted by this final TSAP and the definition of the on-treatment nintedanib phase was adapted to match the definition quoted above.

Further changes compared to the initial TSAP:

- Definition of further safety parameters of interest was added to [Section 5.3.1](#).
- Baseline parameters were added to list of baseline characteristics in [Section 5.4.1](#), respective analyses were added to [Section 7.1](#).
- Definition of nintedanib treatment compliance was added to [Section 5.4.2](#) and its presentation was specified in [Section 7.3](#).
- Definition of nintedanib treatment exposure was revised in Section 5.4.2.
- Definition of AE analysis phases in [Table 6.1: 1](#) and definition of AE collapsing in [Section 7.8.1](#) were adapted to the decision that clock time will not be collected in the eCRF.
- Definition of analysis phases in [Section 6.1](#) was restricted to AE, vital signs and laboratory data, will not be needed for spirometry.
- [Table 6.2: 1](#) was added to specify which important PDs could potentially lead to exclusion from which analysis set.
- Definition of an enrolled set was added to [Section 6.3](#).
- Analyses of AEs by safety topic were added to Section 7.8.1.
- Descriptive analysis of vital signs were added to [Section 7.8.3](#).
- Presentation of pregnancy test results was added in [Section 7.8.5.5](#).
- A few additional clarifications were added, text was adapted to the new BI standard process (e.g., use of a decision log to capture RPM decisions).

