7.8.1 Adverse events

AEs will be coded with the most recent version of MedDRA.

The analyses of AEs will be descriptive in nature. All analyses of AEs will be based on the number of patients with AEs and not on the number of AEs.

For analysis, multiple AE occurrence data on the electronic case report form (eCRF) will be collapsed into one event provided that all of the following applies:

- All AE attributes are identical (lower level term, intensity, action taken, therapy required, seriousness, reason for seriousness, relationship, outcome, AE of special interest (AESI))
- The occurrences were overlapping or adjacent (adjacency of two occurrences is given if the second occurrence started on the same day or on the day after the first occurrence ended)

For further details on summarisation of AE data, please refer to 'Handling and summarisation of adverse event data for clinical trial reports and integrated summaries' ([6](#)) [001-MCG-156 Version 5] and "Handling of missing and incomplete AE dates" ([3](#)) [001-MCG-156_RD-01].

The analysis of AEs will be based on the concept of treatment-emergent AEs. That means that all AEs will be assigned to the screening, treatment or follow-up phases as defined in [Section 6.1](#).

Hepatic injury and gastro-intestinal perforation are defined as protocol-specified AESIs. For details on the definition of hepatic injury see CTP Section 5.2.10.1.4.

According to ICH E3 ([8](#)), AEs classified as 'other significant' need to be reported and will include those non-serious and non-significant AEs with

- (i) 'action taken = discontinuation' or 'action taken = reduced', or
- (ii) marked haematological and other lab abnormalities or leading to significant concomitant therapy as identified by the Clinical Monitor/Investigator at a Medical Quality Review Meeting.

An overall summary of AEs will be presented. This overall summary will comprise summary statistics for the class of other significant AEs according to ICH E3 ([8](#)).

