The frequency of patients with AEs will be summarised by primary system organ class and preferred term. AEs which were considered by the investigator to be drug-related will be summarised separately. Separate tables will also be provided for patients with serious AEs (SAEs), patients with AESIs and patients with other significant AEs (according to ICH E3 ([8](#))). The frequency of patients with AEs will also be summarised by worst common terminology criteria, primary system organ class and preferred term.

The system organ classes and preferred terms within system organ classes will be sorted by descending relative frequency.

In addition, the frequency of patients with AEs, SAEs and drug related AEs will be summarised by safety topic, subcategory and preferred term for the organ systems 'Hepatobiliary' and 'Liver laboratories'. Safety topics and subcategories are defined on project level and stored in PDMP in the TMF ([10](#)). The most recent version of this file will be used for the analysis.

For disclosure of AE data on ClinicalTrials.gov, the frequency of patients with non-serious AEs occurring with an incidence of greater than 5 % (in preferred terms) will be summarised by primary system organ class and preferred term. The frequency of patients with SAEs will also be summarised.

For disclosure of AE data in the European union drug regulating authorities clinical trials (EudraCT) register, the frequency of AEs, the frequency of non-serious AEs with an incidence of greater than 5 % (in preferred terms) and the frequency of SAEs will be summarised.

For support of lay summaries, the frequency of patients with drug-related SAEs will be summarised by treatment, primary system organ class and preferred term.

Details collected in the eCRF regarding bleeding AEs and AEs of diarrhoea will be listed.

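### SAP 7.8.1 tabulates all adverse events by worst CTCAE category, but the protocol asks for CTCAE grading of diarrhoea only, and no named SAP table uses the mild/moderate/severe scale that applies to every event

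*SAP*

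**What the plan says.** Protocol Section 5.2.10.1.5 sets the general scale: "The intensity (severity) of the AE should be judged based on the following", followed by definitions of mild, moderate and severe. It then adds a second scale for one event type: "In addition the intensity of diarrhoea adverse events should be classified and recorded in the eCRF according to the Common Terminology Criteria" for Adverse Events, version 4. The only CTCAE table in the protocol gives grades 1 to 5 for diarrhoea.

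Protocol Section 7.3.4 commits to the output: "Frequency, severity, and causal relationship of adverse events will be tabulated by system organ class and preferred term".

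SAP Section 7.8.1 gives the severity table as follows: "The frequency of patients with AEs will also be summarised by worst common terminology criteria, primary system organ class and preferred term". It also plans that "Details collected in the eCRF regarding bleeding AEs and AEs of diarrhoea will be listed". Intensity appears in that section only in the rule for collapsing repeated records: "All AE attributes are identical (lower level term, intensity, action taken, therapy required, seriousness, reason for seriousness, relationship, outcome", with adverse event of special interest completing the list.

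SAP Section 4 introduces its differences from the protocol with "As compared to the CTP, the following changed in the planned analysis of this study".

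**The concern.** The SAP table and the protocol's data specification use different scales. The SAP classifies all adverse events by a scale that the protocol asks sites to apply to diarrhoea alone. The scale that the protocol applies to every event has no table named in the SAP.

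A programmer who follows SAP 7.8.1 literally would produce a severity table with grades for diarrhoea and no grade for anything else. Protocol Section 1.2.1 describes nintedanib's main risks as gastrointestinal and hepatic, and also names bleeding. Nausea, vomiting, hepatic and bleeding events would then have no named summary on the severity scale defined for them, and the severity tabulation promised in protocol 7.3.4 would have no corresponding SAP output.

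**Working it through.** No figure is at issue, so the check sets the passages side by side.

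**1. Which scale is specified for which events (protocol 5.2.10.1.5)**

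| Scale | Levels | Events covered |
|---|---|---|
| Intensity | 3 (mild, moderate, severe) | every adverse event |
| CTCAE version 4 | 5 (grades 1 to 5) | diarrhoea only, in addition to intensity |

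Elsewhere in the protocol, CTCAE appears only in the abbreviation list and the reference list. No section asks for a CTCAE grade for any other event.

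**2. Which tables SAP 7.8.1 names**

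- an overall summary, described only as including other significant events
- all events by system organ class and preferred term
- drug-related events
- serious events
- events of special interest
- other significant events
- events by worst common terminology criteria
- hepatic safety-topic tables
- registry disclosure tables
- a lay-summary table

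The common terminology table is the only one classified by a severity scale. None is classified by mild, moderate or severe.

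**3. Can the named table be filled?** For diarrhoea, yes. For every other preferred term, the protocol specifies no grade to enter.

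**4. Was a change of scale declared?** SAP Section 4 lists three changes from the protocol: renaming the phase after the residual effect period, not adopting the descriptive group comparison of laboratory data, and settling the purpose of nintedanib trough sampling. None concerns adverse event severity. Among the changes from the initial SAP, two entries touch Section 7.8.1: the collapsing rule, adapted because clock time is not collected, and the safety topics ("Analyses of AEs by safety topic were added to Section 7.8.1"). Neither changes the severity scale.

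**5. What the collapsing rule shows.** It lists nine attributes: lower level term, intensity, action taken, therapy required, seriousness, reason for seriousness, relationship, outcome and special-interest status. One is intensity and none is a CTCAE grade. This is weak evidence about what the eCRF holds, because the diarrhoea grade that the protocol does require is missing from the list too. It does show that the SAP treats intensity as available. It also leaves a gap for diarrhoea itself: two adjacent records with the same nine attributes but different CTCAE grades would be merged, with no rule for which grade is kept.

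**The case against.** The strongest reply is that nothing has been lost. Protocol 7.3.4 still promises the severity tabulation and standard sponsor tables, the SAP describes itself as an elaboration of that protocol section, and SAP Section 4 does not withdraw the promise. SAP 7.8.1 also refers to a sponsor standard (001-MCG-156) for further details of adverse event summarisation, so its list of tables need not be complete. CTCAE grades might be collected for all events in the eCRF. The SAP phrase contains neither the word grade nor the abbreviation CTCAE, so it may be a slip for worst intensity. Finally, this is a small exploratory pharmacokinetic trial (about 24 patients enrolled, 14 evaluable) with descriptive safety analyses, individual listings, and separate tables for serious, special-interest and drug-related events.

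Much of this stands, and it limits the weight of the point. Whether an intensity table will be produced under the standard, and whether other events are graded in the eCRF, cannot be settled from the two documents. But an unseen standard does not correct a sentence that names a table and gives it a scale the protocol does not specify for most events. If the phrase is a slip, it needs correcting; if it is intended, the wider grading and the change of scale need stating. Each reading leads to an edit.

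**Conclusion.** The concern holds. SAP 7.8.1 specifies a severity table for all adverse events on a scale that the protocol specifies for one event type, and it names no table on the three-level scale that applies to every event. No change of scale is declared.

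The textual mismatch is certain. The practical consequence, a table graded for diarrhoea alone, assumes that the eCRF collects what protocol 5.2.10.1.5 describes and no more, and that the SAP is followed literally. It also takes the SAP phrase to mean CTCAE, which is the only common-terminology scale in either document.

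The impact is low and confined to descriptive safety tables. The primary and secondary pharmacokinetic analyses do not depend on it.

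**What to change.** Check first what the eCRF collects, then align the text.

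- **If CTCAE grades are collected for diarrhoea only, as the protocol says:** in the SAP 7.8.1 sentence, replace the common terminology criteria with worst intensity (mild, moderate, severe), keeping system organ class and preferred term. This supplies the severity table promised in protocol 7.3.4. Limit any CTCAE display to diarrhoea; the planned listing of diarrhoea details is sufficient and a table is optional. If a diarrhoea grade table is produced, state how the grade is handled when records are collapsed.
- **If CTCAE grades are collected for all events:** say so in SAP 7.8.1 with the CTCAE version, bring protocol 5.2.10.1.5 into line, and record the change of scale in SAP Section 4.

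The first option costs one sentence of SAP wording and one standard table. It needs no new data, since the protocol specifies intensity for every event and the SAP already uses it to collapse records.

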7.8.2 Laboratory data

The analyses of laboratory data will be descriptive in nature and will be based on BI standards ([7](#)).

Possibly clinically significant abnormalities will be identified based on BI standard rules which are based on normalized converted lab values, i.e. on values transformed to SI units and to a standard reference range. These rules will be listed in the SDL appendix of the CTR. Frequency tables will summarize the number of patients with possibly clinically significant abnormalities.

All individual laboratory data will be listed. Values outside the reference range will be flagged. In addition, possibly clinically significant values will be flagged in the listing.

Clinically relevant findings in laboratory data, as judged by the investigator, were to be reported as baseline conditions (if condition already existed before intake of first study drug) or as AEs (during the trial), and will be analysed as such.

7.8.3 Vital signs

Summary statistics will be presented for observed values and change from baseline.

The frequency of patients with marked changes in vital signs will be summarised according to the definitions in [Section 5.3.1](#) of this document.

Clinically relevant abnormal findings in vital signs data, as judged by the investigator, were to be reported as baseline conditions (if condition already existed before intake of first study drug) or as AEs (during the trial) and will be analysed as such.

7.8.4 ECG

Clinically relevant abnormal findings in electrocardiogram (ECG) data, as judged by the investigator, were to be reported as baseline conditions (if condition already existed before intake of first study drug) or as AEs (during the trial) and will be analysed as such.

7.8.5 Others

7.8.5.1 Spirometry

With regard to spirometry, the highest FVC and highest FEV1 each obtained on any of three efforts which meet the criteria of the American Thoracic Society and European Respiratory Society – with preferably a maximum of five manoeuvres – were to be recorded in the eCRF.

Spirometry data (except for baseline data) will only be listed.

Clinically relevant abnormal changes in spirometry data, indicative of worsening of lung function since baseline, as judged by the investigator, were to be reported as AEs and will be analysed as part of AE analysis.

7.8.5.2 Body weight

Body weight (at screening and end of study visit) will be listed.

7.8.5.3 Physical examination

Physical examination abnormal findings were to be reported as relevant medical history/baseline condition (if condition already existed before intake of first study drug) or as AE and will be summarised as such. No separate listing or analysis of physical examination findings will be prepared.

7.8.5.4 Doppler echocardiography

Clinically relevant abnormal findings in Doppler echocardiography were to be reported as relevant medical history/baseline condition (if condition already existed before intake of first study drug) or as AEs and will be analysed as part of AE analysis.

7.8.5.5 Pregnancy test

Pregnancy test results (as reported in the eCRF) will be listed.

10. HISTORY TABLE

Table 10: 1 History table

Version	Date (DD-MMM- YY)	Author	Sections changed	Brief description of change
Initial	11-OCT-2018		None	This is the initial TSAP with necessary information for trial conduct
Final	08-NOV-2019		See Section 4 for a summary of changes	This is the final TSAP
